3.2 Study Endpoints

3.2.1 Safety Endpoints

The safety endpoints are:

- 1) Adverse events
- 2) Adverse events that preclude further treatment with the study agent
- 3) Serious hypotension defined as hypotension requiring hospitalization or treatment in an emergency room and not attributable to overt sepsis, acute myocardial infarction, or other cardiovascular event (e.g. aortic dissection)
- 4) Recurrent intra-dialytic hypotension is defined as systolic blood pressure <80 mm Hg during ≥3 dialysis sessions per rolling 30-day period or treatment for either hypotension or symptoms of hypotension if systolic blood pressure is <100 mm Hg during ≥3 dialysis sessions per rolling 30-day period. Treatment includes saline infusion, lowering of the ultrafiltration rate or other

interventions directed at hypotension such as vasopressor agents. Symptoms include but are not limited to muscle cramping, lightheadedness, and nausea.

- 5) Inter-dialytic hypotension defined as systolic blood pressure <90 mm Hg or hypotension requiring adjustment in blood pressure medications or treatment in an emergency or hospitalized setting.
- 6) Mean pre-dialysis blood pressure
- 7) Mean lowest intra-dialytic blood pressure
- 8) Cardiovascular hospitalization
- 9) Stroke
- 10) Death

3.2.2 Tolerability Endpoints

Tolerability will be assessed on the basis of whether participants can continue the assigned dose throughout the entire treatment period. Failure of overall tolerability will be defined by discontinuation or reduction in dose of study medication. Tolerability events will be sub-classified according to whether discontinuation is due to gastrointestinal symptoms or headache.

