2.1 Primary Objectives

Safety

- To evaluate the safety of ISD/HY therapy in individuals with ESRD on HD.
 - Safety events include the following:
 - Serious hypotension is defined as hypotension requiring hospitalization or treatment in an emergency room and not attributable to overt sepsis, acute myocardial infarction, or other cardiovascular event (e.g. aortic dissection)
 - Inter-dialytic hypotension
 - Intra-dialytic hypotension and symptoms of hypotension (e.g., muscle cramping)
 - Treatment-emergent events defined as the combined incidence of death, myocardial infarction, stroke, hospitalizations, , and serious hypotension (hypotension requiring hospitalization or treatment in an emergency room and not attributable to overt sepsis, acute myocardial infarction, or other cardiovascular event)
 - The individual components of the treatment-emergent endpoint
 - Cardiovascular death
 - Gastrointestinal events or headache requiring dose adjustment or discontinuation

Tolerability

- To evaluate the tolerability of assigned therapy in individuals with ESRD on maintenance hemodialysis. Tolerability events will include reduction in dose of study medication during the course of the treatment period or discontinuation of study drug.

Efficacy

- To test the hypothesis that ISD/HY combination therapy improves diastolic function in individuals with ESRD on HD compared with placebo. The change in E' on TDI echocardiography of the left ventricle from baseline to end of study will be used in the primary endpoint assessment of diastolic function.
- To test the hypothesis that ISD/HY combination therapy improves microvascular function in individuals with ESRD on HD compared with placebo. The change in CFR on myocardial PET from baseline to end of study will be used for the primary endpoint assessment of diastolic function.

Feasibility

- To assess feasibility of conducting a full-scale trial.
 - Feasibility will be assessed based on recruitment rate and dropout rates.

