3.1 General Design

[figure not shown]
This is a randomized, placebo-controlled 2-arm trial that will compare placebo with ISD/HY combination therapy. Participants will be randomized in a 1:1 fashion to ISD/HY or placebo. As shown in Figure 4, the study will be conducted in 2 phases: a 4-week dose escalation phase and a 22-week treatment phase.

All randomized participants will initiate treatment with therapy three times daily. The active therapy group will receive a one-week supply of ISD/HY 10/10 followed by a one-week supply of ISD/HY 20/35 3x/day. The placebo control group will receive an identical supply of placebo and will follow the same

schedule as the active therapy group. At the 1 week and the 2 week visits, tolerability and hypotension will be assessed. If the starting dose and first dose titration is tolerated, participants will be increased to ISD/HY 40/75 mg 3x/day (active therapy) or placebo and they will receive an additional 2 weeks drug supply. Tolerability will be re-evaluated after an additional 2 weeks and at 4 week intervals thereafter. At 4 weeks, participants tolerating the full dose will receive a 12-week supply of study medication at the appropriate dose. At 16 weeks, an additional 10-week supply will be provided. Participants not tolerating the full dose at this point may reduce to the starting doses of active therapy at this visit. In the event of poor tolerance or drug related adverse events (e.g. hypotension, intra-dialytic cramping), the dose of study medication may be held or reduced to a minimum dose of ISD/HY 10/10 mg 3x/day (active therapy) or matched placebo 3x/day. Except where un-blinding is necessary for safety purposes, participants not tolerating the lowest dose of active therapy will be reduced to double placebo therapy in order to maintain unbiased assessments of study endpoints.

In order to maintain the blind, all study participants, regardless of randomized assignment, will receive new dosing kits within 1 day (with a window of up to 3 days) of the 1, 2, 4, and 16 week visits, and will be evaluated bi-weekly during the dose escalation phase.

Figure 4. Study Design

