5.2 Treatment Regimen

As depicted in Figure 4, 16 participants will be randomized in a 1:1 fashion to either placebo 3x daily or ISD/HY 10 mg/10 mg, 3x daily for 1 week. Doses scheduled to be administered within 2 hours prior to a dialysis session will be held and administered post-dialysis on dialysis days. Participants will be contacted by phone or in person to review tolerability and adverse events at 1 week after drug initiation and will be examined in person at 2 weeks. Dialysis records will be reviewed for hypotension at each visit. The sequence will be repeated following the scheduled dose titration which will occur following the 2-week visit. Adjustment to dosage of concomitant medications, the dialysis prescription, or the study drug on the basis of hypotension will occur as described in Section 6.7.

All randomized participants will receive an initial one-week supply of study medication following the baseline visit, and a one-week supply after the Week 1 visit. Those assigned to ISD/HY will begin treatment at 10/10 mg 3X daily. Participants randomized to placebo will follow the identical schedule. Participants will be contacted at 1 week to check for the occurrence of adverse events and dose-limiting symptoms, and those tolerating the study drug will have the dose increased to ISD/HY 20/35 mg 3X daily or placebo. At Week 2 participants will be examined in-person at their dialysis units. Adverse events will be reviewed and dialysis run sheets will be examined for the occurrence of inter- or intra-dialytic hypotension at each visit. In the absence of dose-limiting hypotension or other adverse events, the dose of ISD/HY will be increased to 40/75 mg 3X/daily following the Week 2 visit.

During the 4-week dose escalation phase, a study drug request form will be entered into the data management system at 1 week, 2 weeks and 4 weeks to request the next supply of study drug. Unless there is a contraindication to a dose increase (e.g. hypotension), the investigator will indicate approval for dose escalation on the request form. The Data Management System will generate a unique kit number based on the randomized treatment assignment and the prior dose. If up-titration to the next dose is contraindicated, the Clinical Center investigator will indicate this on the study drug request form and a kit number corresponding to the current dose of will be generated.

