If down-titration of the study drug dose is required during the dose escalation phase or during the treatment phase, the Clinical Center investigator will request a dose reduction on the study drug request form. In this case, a supply of blinded study medication using the next lower dose of ISD/HY or placebo will be provided. In the event that a participant is already receiving the lowest dose, study medication will be discontinued. In the event that a 3rd down titration of dose is required study medications will also be discontinued. Un-blinding to preserve patient safety will be considered via a formal request to the DCC.

If the dose escalation schedule is interrupted (e.g., if a participant is hospitalized at the scheduled time of dose escalation and did not take study drug during the hospitalization), dose escalation will be delayed until the participant has had access to the current dose of study drug for the specified interval (1 week for the first dose level, 2 weeks for the second dose interval). If, due to a considerable delay in dose escalation, a participant has not reached the final dose assignment by their Week 8 visit, the participant will remain at the current dose of study drug for the remainder of the study and the treatment phase will be shortened accordingly such that the total duration of study participation is not increased as a result of the delay. For example, if dose escalation is not completed until week 10, the treatment phase will be 16 weeks rather than 22 weeks.

Participants will be contacted by phone or in person at Weeks 1 and 3 (plus or minus 3-5 days) as described above and will be examined in-person at Weeks 2 and 4. Dialysis records will be reviewed at each time point. Following the Week 4 visit a 12-week supply of the maximal tolerated dose of study medication will be distributed to participants who will be evaluated in-person at the dialysis unit every 4 weeks for the duration of the study. A 10-week supply of study medication will be distributed to participants following the Week 16 visit. At Week 26, participants will have a close-out visit, echocardiography and PET scan at the medical center and will then discontinue study medications.

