In the event of dose-limiting symptoms such as headache, hypotension or gastrointestinal distress, dose increases will be deferred until symptoms have resolved and there has been adjustment to concomitant therapies, diet or dialysis prescription as described in Section 6.7, the dose of study medication or matched placebo may be reduced as applicable. During both the dose escalation phase and the treatment phase, the dose may be reduced to the next lower dose level in the event of adverse events as described in Section 6.7. In order to maintain the blind, all participants will receive blinded medication supplies according to the specified dose within 3 days of the Week 1, Week 2 and Week 4 visits, and within 1 week of the Week 16 week visit, regardless of whether the dose is changed.

Method for Assigning Participants to Treatment Groups

The randomization schedule will be stratified by left ventricular ejection fraction (LVEF) at $\leq 45\%$ vs $> 45\%$ to ensure balance across treatment arms of patients with preserved versus reduced LVEF. A clinical echocardiogram will be used for LVEF determination if available within 6 months. If no echocardiogram is available within the required timeframe then a study cardiologist will perform a limited reading on the study echocardiogram done during the baseline visit. There may be a delay of up to 72 hours between the baseline visit and randomization to allow for the completion of this limited reading.

Randomly permuted blocks of random sizes will be used to control the balance of participants assigned to each treatment regimen within each stratum. This method guarantees that at no time during randomization will the number of participants in any arm be grossly imbalanced, and ensures that the investigator will be unable to predict assignments. All randomization schedules will remain confidential, and known only to authorized members of the central pharmacy.

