5.3 Preparation and Administration of Study Drug and Maintenance of Blind

Study drug and matching controls will be prepared by the Investigational Drug Service (IDS). The IDS will distribute study drug kits, containing a 1-week supply at baseline and Week 1, a 2-week supply at Week 2, a 12-week supply at Week 4, and a 10-week supply at Week 16. Drug supplies will be packaged to contain a 3-day or 5-day supply of extra medication depending on the visit interval.

All doses of ISD, HY, and placebo will be manufactured to have identical appearances using gelatin encapsulation or equivalent methods. IDS personnel responsible for preparation of study drug will not have access to study data or results and will not participate in analyses of study data or publications. However, appropriate IDS personnel will have access to the randomization scheme and code in order to prepare study drug kits containing the correct dose of active medication or placebo for each group and study participant.

During the dose titration phase, IDS personnel will prepare kits containing a 10-day supply of the specified dose of ISD/HY or matched placebo for each group at baseline and Week 1. These packages will be replaced with kits containing a 2-week + 5 day supply of the next dose of study drug or placebo following the Week 2 visit, a 12-week + 5 day supply following the Week 4 visit, and a 10-week + 5 day supply following the Week 16 visit. If up-titration to the next dose is not indicated (e.g. due to hypotension or gastrointestinal symptoms), the investigator will notify the IDS, and a package containing

the last dose of ISD/HY or placebo will be substituted. If at any time, the participant experiences dose-limiting symptoms requiring down-titration of study drug, the IDS will be notified to prepare a new supply of study drug at the next lowest dose for the appropriate number of days remaining until the next scheduled drug distribution. The participants will be instructed to discontinue study medication until they receive the new package.

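### The tolerability failure rule omits escalation withheld for symptoms, and contradicts the sentence before it if the undefined assigned dose means the target dose

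*Combined protocol and SAP*

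**What the plan says.** Section 3.2.2 has two sentences that bear on the point. The first gives the concept: "Tolerability will be assessed on the basis of whether participants can continue the assigned dose throughout the entire treatment period". The second gives the rule: "Failure of overall tolerability will be defined by discontinuation or reduction in dose of study medication". The assigned dose is not defined. Section 2.1 names the same events: "Tolerability events will include reduction in dose of study medication during the course of the treatment period or discontinuation of study drug". The sub-classification in 3.2.2 names gastrointestinal symptoms and headache only. The Study Summary describes tolerability differently again, as adherence to treatment.

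The dosing sections provide for a participant who is neither reduced nor stopped but does not go up:

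- Section 5.2: "If up-titration to the next dose is contraindicated, the Clinical Center investigator will indicate this on the study drug request form", and a kit at the current dose is then issued.
- Section 5.2, for dose-limiting symptoms: "dose increases will be deferred until symptoms have resolved".
- Section 5.3: "If up-titration to the next dose is not indicated (e.g. due to hypotension or gastrointestinal symptoms), the investigator will notify the IDS", and the pharmacy supplies the previous dose again.
- Section 5.2, for a participant not at the final dose by Week 8 after a long delay in escalation: "the participant will remain at the current dose of study drug for the remainder of the study".

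After Week 4, section 5.2 dispenses a 12-week supply of whatever dose is the highest tolerated, which may be below 40/75 mg. Section 3.1 adds a further possibility: "the dose of study medication may be held or reduced to a minimum dose of ISD/HY 10/10 mg 3x/day". A hold is not named in the failure rule either.

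**The concern.** Sections 3.1, 5.2 and 6.4 make each dose increase conditional on tolerating the current dose. A participant refused an increase because of hypotension is therefore treated as not tolerating the regimen when drug is dispensed, yet is not a failure when the endpoint is scored. The ordering can also invert: someone who never leaves 10/10 mg because of symptoms scores better than someone who reaches 40/75 mg and later takes one step down.

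This matters because the trial's declared value lies in its estimates for planning later studies (sections 7.1 and 7.4). A full-scale trial needs to know how many dialysis patients reach the target dose and stay on it. The endpoint as defined cannot say, and hypotension, the subject of its own procedure in section 6.7, is missing from the listed reasons.

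**Working it through.** **Inputs.** Eight participants per arm (section 7.1). Failure events: discontinuation or reduction (sections 2.1 and 3.2.2). Number of participants whose escalation is blocked: not given anywhere, so assumed below.

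**Step 1. Apply both sentences of 3.2.2 to the courses the protocol allows.**

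| Course to Week 26 | Reduced or stopped? | Failure sentence | First sentence, if assigned dose = 40/75 |
|---|---|---|---|
| Reaches 40/75 and stays | No | Not a failure | Tolerates |
| Held at 10/10 for hypotension | No | Not a failure | Does not tolerate |
| Held at 20/35 for symptoms | No | Not a failure | Does not tolerate |
| Reaches 40/75, steps down once | Yes | Failure | Does not tolerate |
| Stopped at 10/10 | Yes | Failure | Does not tolerate |

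The sentences disagree in rows 2 and 3. If the assigned dose means the dose currently dispensed, they agree, but rows 2 and 3 then count as tolerating.

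**Step 2. Reproduce the plan's own figures for event rates.** Table 2 is the chance of at least one event in 8, 1 − (1 − p)^8. For p = 0.05, 0.10, 0.15, 0.20, 0.25 and 0.30 this gives 0.337, 0.570, 0.728, 0.832, 0.900 and 0.942, matching every printed row. Table 1 is the exact (Clopper-Pearson) interval: lower limit = Beta quantile at 0.025 with parameters (x, 9 − x), upper limit = Beta quantile at 0.975 with parameters (x + 1, 8 − x). It reproduces for 0, 1, 5 and 8 events. For 2/8 the lower limit computes to 0.032, while Table 1 prints 0.32, which lies above the observed 0.25. That is a separate error; 0.03 is used here.

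**Step 3. Size in one arm.** Each blocked participant who is never reduced or stopped moves the rate by 1/8 = 12.5 percentage points.

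| Assumed course in the arm | Rate under the rule (95% CI) | Rate counting blocked participants (95% CI) |
|---|---|---|
| 2 blocked, 0 reduced or stopped | 0/8 = 0% (0 to 0.37) | 2/8 = 25% (0.03 to 0.65) |
| 3 blocked, 0 reduced or stopped | 0/8 = 0% (0 to 0.37) | 3/8 = 37.5% (0.085 to 0.755) |
| 2 blocked, 1 reduced | 1/8 = 12.5% (0.003 to 0.527) | 3/8 = 37.5% (0.085 to 0.755) |

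**Step 4. The same on the scale of Table 2.** Suppose 10% of participants truly reduce or stop and a further 20% are only blocked. The chance of scoring at least one failure in an arm is 1 − 0.9^8 = 0.57 under the rule and 1 − 0.7^8 = 0.94 when blocked participants count. With 5% and 5% it is 0.34 against 0.57.

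**Step 5. Check whether another measure fills the gap.** Pill counts (5.4) and the per-protocol threshold of 75% (7.3) are set against prescribed doses, so a participant held at 10/10 mg can be fully adherent. The safety item in 2.1 on dose adjustment covers gastrointestinal events and headache, not hypotension. As-treated analyses (7.3) use the dose actually received, but for efficacy and safety, not for the tolerability rate.

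**The case against.** The strongest reply is that the design titrates each participant to tolerance, so staying on one's individual dose is a legitimate endpoint. That is fair as a description: escalation needs investigator approval and is not forced. But then 3.2.2 should say that the assigned dose is the individual's dose, and the report should still show which dose that was.

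Second, the text is not closed. The first sentence of 3.2.2 may refer to the target dose, and 2.1 says events will include the two named, which need not be exhaustive. So a reader might infer that the plan unambiguously scores a blocked participant as tolerating. The documents do not support quite that: the explicit failure rule does so, while the sentence before it may not. The ambiguity itself needs resolving.

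Third, a reader might infer that escalation removes the least tolerant participants before they can be scored. It does not. They stay in the intention-to-treat population, and anyone stopped at the lowest dose is a failure. The gap concerns only those who remain on drug below target.

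Fourth, much of the information exists elsewhere. Recurrent intra-dialytic and inter-dialytic hypotension are safety endpoints (3.2.1), the Study Summary lists dosing completeness under feasibility, and the drug request form shows refused increases. This limits the harm and makes the repair cheap, but it leaves the tolerability rate as it is.

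Finally, blocking may be rare, since entry requires systolic pressure of at least 120 mm Hg and section 6.7 tries other measures before reducing study drug. Nothing in the documents settles this.

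**Conclusion.** The concern holds as a gap and an unreconciled definition on a primary objective. Relative to a rule that counts withheld escalation, an arm's failure rate can be understated but not overstated, by 12.5 points for each participant blocked to Week 26 and not otherwise reduced or stopped. The 2/8 and 3/8 cases and the percentages in step 4 illustrate this with assumed counts and rates; they are not forecasts.

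A reader might also infer that the shortfall falls on the active arm alone. That does not follow: section 8.3.2 describes hypotension around dialysis as frequent in this population, so placebo participants may be blocked too, and the effect on the difference between arms is not determined. Nor does the point undermine the trial. Section 7.1 already calls these estimates crude, the intervals at n = 8 overlap widely, and no go/no-go rule is tied to tolerability. What is at stake is whether the pilot reports the tolerability figure that a larger trial would need.

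**What to change.** Change the wording before analysis:

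1. Define the assigned dose, and make 2.1, 3.2.2 and the Study Summary agree.
2. Keep any discontinuation or reduction as a failure, whatever its cause. Adding a causality condition would narrow the present rule and drop some failures it now counts, such as study drug withdrawn on starting sildenafil (5.5).
3. Add as a failure: escalation withheld for symptoms, with the target dose or matching placebo level never reached during the treatment period. State also how a temporary hold is scored.
4. Report by arm the proportion reaching each dose level and the proportion still on it at Week 26.
5. Add hypotension to the sub-classified reasons.

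The new criterion should not rest on the Week 8 provision in 5.2. That text fixes the dose for participants who have not reached the final level by Week 8, yet its own example has escalation completed at week 10. The two must be reconciled separately; no dosing rule is proposed here.

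The cost is a few lines and one table, with no added visits. The tolerability rate may look less favourable. Section 5.2 has the request form record that an increase is contraindicated but does not say it records why, so the reason may have to be linked from the adverse event log.
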